24 mg/6 mg of buprenorphine/naloxone. If run-in criteria are met, each subject will continue dosing with their stabilized dose of SUBOXONE SL film after the run-in period for required inclinic dosing. Qualifying subjects will continue to Day 1, where SUBOXONE SL film dosing alone continues for 2 more days. On Day 3, subjects will begin receiving doses of both SUBOXONE SL film and INDV-2000 for 7 days. Starting on Day 10, subjects will stop dosing with SUBOXONE SL film and dose with INDV-2000 alone for 4 more days and remain in clinic until completion of assessments on Day 14. Rescue medications to treat opioid withdrawal signs and symptoms will be allowed in the study based on Investigator's medical judgment. After assessments are completed on Day 14, subjects can begin a standard of care treatment for OUD. The EOS visit is scheduled for Day 21. If at any stage of the study a subject discontinues, they will be given options for their continued treatment for OUD by the clinical facility.

A schematic depicting the study design is in Figure 1.

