8.4 Vital Signs

Blood pressure, heart rate, respiratory rate and temperature will be measured by automated recorders after the subject has been in a semi-recumbent position for a minimum of 3 minutes according to the time schedule presented in the Schedule of Events tables (Section 22.1, Appendix 1, Section 22.2, Appendix 2 and Section 22.3, Appendix 3). Blood pressure will be measured 3 times (at least 1 minute apart) pre-dose and the mean of the triplicate measures of blood pressure will define baseline SBP and DBP at the pre-dose timepoint.

If a subject shows an abnormal assessment at any stage, a triplicate blood pressure measure will be taken at that timepoint, and the mean of the triplicate measures will be used for any subject discontinuation decisions. The abnormality will be followed to resolution if required. Additional measurements may be taken as deemed necessary by the Investigator (See Section 6.5.1.1).

Any clinically significant abnormalities, including changes from baseline, must be reported as AEs.

Pending emerging data, any changes in the timing or addition of time points for any planned study assessments must be documented and approved by the relevant study team member and then archived in the Sponsor and site study files, but will not constitute a protocol amendment. The IRB will be informed of any safety issues that require alteration of the safety monitoring scheme or amendment of the ICF.

8.5 12-Lead Electrocardiograms

A 12-lead ECG will be recorded after the subject has been in the semi-recumbent position for a minimum of 5 minutes as presented in the Schedule of Events tables (Section 22.1. Appendix 1, Section 22.2, Appendix 2 and Section 22.3, Appendix 3).

[figure not shown]
A triplicate ECG will be recorded for the determination of the baseline result at pre-dose on Day 1. For each numeric ECG parameter, the baseline value will be the mean of the 3 recordings.

If a potentially clinically significant abnormality is noted during other ECG assessments, a triplicate ECG will be taken at that timepoint, and the mean of the triplicate measures will be used for any subject discontinuation decisions. All triplicate ECG recordings should occur at least 1 minute apart. If a subject shows an abnormal assessment at any stage, repeat measurements may be made and the abnormality followed to resolution, if required. Additional measurements may be taken as deemed necessary by the Investigator (See Section 6.5.1.1).

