14 STATISTICS

14.1 General Procedures

This section describes the sample size, analysis populations and planned analyses for primary, secondary and exploratory endpoints and for safety assessments. A comprehensive statistical analysis plan (SAP) will be developed to detail the statistical methodology for all aspects of the planned analyses. The SAP will be approved after the protocol is finalized and before the database is locked. Any deviations from the analyses described below will be identified in the SAP (and subsequently the CSR). Any unplanned analyses not described in the SAP will be identified in the CSR.

Data will be listed and summarized separately for Parts I, II and III of the study. For Parts I and II, data will be summarized by dosing cohort for active treatment and for placebo subjects combined over all dosing cohorts. Continuous variables will be summarized using descriptive statistics such as means, standard deviations (SD), medians, minimums and maximums. Categorical variables will be reported as frequency counts and the percentage of subjects in corresponding categories. Individual subject data will be presented in data listings. Data listings will include all data collected from enrolled subjects.

For change from baseline calculations, baseline will be defined as the last measurement taken prior to administration of IMP (INDV-2000 or placebo for Parts I and II, and INDV-2000 for Part III). For blood pressure and numeric ECG parameters, triplicate means will be used for baseline.

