14.9.3 Vital Signs

Vital signs (blood pressure, heart rate, respiratory rate, temperature) will be summarized as observed values and changes from baseline by analysis visit. For SBP and DBP, baseline will be defined as the mean of triplicate measurements.

Confidential Page 69 of 108

INDV-2000 Indivior Clinical Study Protocol: INDV-2000-102 09 May 2023

14.9.4 12-Lead Electrocardiogram

Numeric 12-lead ECG parameters will be summarized as observed values and changes from baseline by analysis visit, with baseline defined as the mean of triplicate measurements. ECG interpretation will be summarized by visit as a categorical variable, with baseline interpretation defined as the majority of the triplicate assessments; if there is no majority, the Sponsor will be notified and will provide a baseline interpretation based on a review of the data.

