### **5.1.5. Definitions**

IMP: INDV-2000 or placebo (placebo not applicable in Part III)

---

Study Drug: INDV-2000, SUBOXONE SL film, or placebo (placebo not applicable in Part III).

Screening Period: Informed consent to Day -7 Clinic Check-In.

Run-In Period: Day -7 to Day -1 Run-In Assessment

End-of-Study (EOS): Early termination or completion of last scheduled visit.

Enrolled Subject: Met Day -1 run-in assessment criteria.

Study Day 1: day of first dose of study drug administration after the run-in period.

Study day:

- Study day = date of assessment – date of Study Day 1 + 1, for assessments on or after Study Day 1
- Study day = date of assessment – date of Study Day 1, for assessments before Study Day 1

Study time: time of assessment – time of first study drug administered in the clinical unit.

Duration:

- Duration in days = end date – start date + 1
- Duration in minutes = end time – start time. Durations will be adjusted for Daylight Saving Time, where applicable.

Baseline observation: for a given parameter for a given subject, the last observed value, including unscheduled and repeated assessments, before the first dose of IMP or planned first dose of IMP if IMP was not administered.

Run-in baseline observation: for a given parameter for a given subject, the last observed value, including unscheduled and repeated assessments, before the first dose of study drug during the run-in period.

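### Part III BP and ECG baseline: the visible SAP rule takes the last single value, while the protocol requires a triplicate mean (majority for ECG interpretation), and the baseline occasion is not settled

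*SAP*

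**What the plan says.** **Protocol, statistics.** Section 14.1 gives a general rule, "baseline will be defined as the last measurement taken prior to administration of IMP", and names INDV-2000 as the IMP for Part III. It then adds: "For blood pressure and numeric ECG parameters, triplicate means will be used for baseline". Section 14.9.3 repeats this for BP: "For SBP and DBP, baseline will be defined as the mean of triplicate measurements". Section 14.9.4 does the same for numeric ECG and treats ECG interpretation separately, "with baseline interpretation defined as the majority of the triplicate assessments".

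**Protocol, procedures.** Section 8.5 states: "A triplicate ECG will be recorded for the determination of the baseline result at pre-dose on Day 1". Section 8.4 says that "the mean of the triplicate measures of blood pressure will define baseline SBP and DBP at the pre-dose timepoint", but names no day. Footnotes 7 (BP) and 8 (ECG) to the Part III schedule (22.3.2) place the triplicates at Day 1 pre-dose, and otherwise only as needed to assess stopping criteria.

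**First INDV-2000 dose in Part III.** Section 4.1: "On Day 3, subjects will begin receiving doses of both SUBOXONE SL film and INDV-2000 for 7 days".

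**SAP.** Section 5.1.5 defines baseline for any parameter as "the last observed value, including unscheduled and repeated assessments, before the first dose of IMP". Section 6.3 (Appendix 3) keeps the most recent non-missing assessment when a visit has more than one. Sections 5.5.3.2 and 5.5.3.3 summarise change from baseline, and shift for ECG interpretation, without mentioning triplicates. Section 1 says that the SAP supersedes the protocol's statistical text and that differences are identified in Appendix 2. The visible entries there are two added populations.

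**The concern.** The two documents give different baselines for the same tables. The protocol averages three readings, or takes the majority of three interpretations. The visible SAP text takes the last record. Even if a triplicate were taken immediately before INDV-2000, the SAP wording would select its final reading and discard the averaging.

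The schedule adds a second difficulty. In Parts I and II the same triplicate sentence works, because IMP starts on Day 1. In Part III the triplicate comes two days before INDV-2000, with single readings in between.

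Part III has no placebo group. Change from baseline is therefore the main way to read BP and QTcF on INDV-2000, alone and with SUBOXONE, and readers of those tables need to know what they are measured against.

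**Working it through.** The plan gives no figure to reproduce on this point. The check is a schedule trace, followed by an illustration under assumed inputs.

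**1. Readings before the first INDV-2000 dose (Part III footnotes 7 and 8)**

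| Occasion | BP | ECG |
|---|---|---|
| Day 1 pre-dose | triplicate | triplicate |
| Day 2, 2 h post-dose | not needed for the trace | single |
| Day 2, 4 h post-dose | single | none |
| Day 3 pre-dose | depends on how footnote 7 is read | single |

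Footnote 7 can be read as attaching the pre-dose time to Day 1 only or to every listed day.

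**2. Applying each rule**

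- *SAP 5.1.5, ECG:* the single Day 3 pre-dose tracing.
- *SAP 5.1.5, BP:* a single reading at Day 3 pre-dose or, if none is taken, at Day 2, 4 h post-dose. With morning doses 24 h apart, the latter is 24 − 4 = 20 h before INDV-2000.
- *Protocol, reading A:* the triplicate sentence in 14.1 is an exception to the last-value rule. Baseline is the Day 1 triplicate mean. Section 8.5 supports this for ECG.
- *Protocol, reading B:* both rules apply together. No Part III reading that the footnotes schedule is both a triplicate and the last before INDV-2000.

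The visible SAP text matches neither reading. The Day 1 triplicate stays in the listings and by-visit summaries, but SAP 6.3 as written would keep one reading of the three.

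**3. Illustration of precision (all inputs assumed)**

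Set the within-subject variance to 1. Let *s* be the share that arises within an occasion (between replicates), and let ρ be the correlation between the Day 3 pre-dose and post-dose occasion effects. Day 1 is taken as independent of Day 3, and the post-dose value is one reading.

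- Day 3 baseline of *k* readings: Var(change) = 2(1 − s)(1 − ρ) + s + s/k
- Day 1 triplicate mean: Var(change) = 2(1 − s) + 4s/3

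*Single against triplicate on the same occasion, ρ = 0.* The variances are 2 and 2 − 2s/3, so the SD ratio is 1/√(1 − s/3). For mean change, 16 subjects give the precision of 16(1 − s/3).

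| s | SD ratio | 16 subjects act as |
|---|---|---|
| 0.25 | 1.044 | 14.7 |
| 0.50 | 1.095 | 13.3 |
| 0.75 | 1.155 | 12.0 |
| 1.00 | 1.225 | 10.7 |

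*Day 3 single (visible SAP) against Day 1 triplicate mean (protocol, reading A), for change on Day 3.* Setting the two variances equal gives ρ = s/[3(1 − s)], which is 0.11, 0.33 and 1.00 for s = 0.25, 0.50 and 0.75. Above that correlation the single Day 3 reading is the more precise. At s of 0.75 or more it never is.

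*Example, s = 0.5, ρ = 0.4:*

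- Day 3 single: 2(0.5)(0.6) + 0.5 + 0.5 = 1.600, SD 1.27
- Day 1 triplicate: 1 + 0.667 = 1.667, SD 1.29
- Day 3 triplicate: 0.6 + 0.5 + 0.167 = 1.267, SD 1.13

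The Day 3 triplicate variance differs from the Day 1 triplicate variance by −2(1 − s)ρ, so it is never larger when ρ ≥ 0.

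**4. ECG interpretation (assumes two categories and independent misreads)**

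If each tracing is misread with probability *q*, a majority of three is wrong with probability q²(3 − 2q).

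- q = 0.1: majority 0.028. Of 16 baselines, 0.45 are wrong by majority and 1.6 with one tracing.
- q = 0.2: majority 0.104. Of 16 baselines, 1.66 are wrong by majority and 3.2 with one tracing.

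**The case against.** **The protocol is not contradictory.** The triplicate sentence in 14.1 follows the general rule and names only BP and numeric ECG, so it reads naturally as an exception. Section 8.5 says outright that the Day 1 ECG triplicate determines baseline. This stands: a reader might infer that the protocol's two rules are irreconcilable, and the text does not force that. Section 8.4 also names no day, so BP triplicates at Day 3 pre-dose are a possible reading. An unscheduled Day 3 triplicate, prompted by an abnormal reading, would meet both rules for that subject. None of this removes the conflict with SAP 5.1.5, which would take the last reading of any such set.

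**The SAP governs and selects one record.** This also stands. A reader might infer that two programmers working from the SAP would choose different baselines. Among collected single readings its rule picks one; the doubt in footnote 7 is about what is collected.

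**A rule may exist elsewhere.** Part of SAP 6.4.3 is redacted, Appendix 2 may not be fully visible, and table specifications are a separate document. The point is therefore limited to the visible text.

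**The size is not the size of the harm.** The 4% to 22% compares a single reading with a Day 3 triplicate that the Part III footnotes do not schedule. Against the Day 1 triplicate, the example above slightly favours the SAP's choice. The ECG figures use two categories where the SAP has three, and tracings about a minute apart may share errors, which would shrink the gain from a majority.

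**Little depends on it.** All analyses are descriptive. Part III ECG stopping criteria use absolute QT and QTcF values, there is no BP criterion, and observed values are also tabulated.

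**Conclusion.** The point holds as a discrepancy between SAP and protocol, made harder to resolve by the Part III schedule. The visible SAP rule replaces a triplicate mean or majority with the last single value, and no visible Appendix 2 entry records this.

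The effect is confined to the descriptive BP and ECG change-from-baseline tables and the ECG interpretation shift table. TEAE endpoints and discontinuation decisions are unaffected.

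The documents give no variance components, so the loss of precision is unknown. The 4% to 22% increase in SD of change rests on assumed within-occasion shares of 25% to 100% and independent occasions. It measures what a triplicate on the same occasion would gain. A reader might infer that the SAP's single Day 3 reading is noisier than the protocol's Day 1 triplicate. The documents do not support that: the ordering depends on unknown correlations and can go either way. The correction is worth making because it is cheap and Part III has no control group.

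**What to change.** **In the SAP, in any case.** In 5.1.5 and 6.3, treat a replicate BP or ECG set at one time point as its mean, with ECG interpretation by majority as in protocol 14.9.4. Name one Part III BP and ECG baseline occasion, in the same terms as the protocol.

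**If collection is still open**, choose one:

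- state that the Day 1 triplicate mean is the baseline; or
- preferably, schedule the triplicate at Day 3 pre-dose, before INDV-2000, for Part III only (footnotes 7 and 8, with a Part III limit in 8.5, which is not specific to one part). Under the assumptions above this is at least as precise as either alternative for any correlation of 0 or more.

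In both cases, make clear in footnote 7 whether Day 3 pre-dose vital signs are taken.

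**If collection is complete**, list the departure from the triplicate mean in Appendix 2, and show change from the Day 1 triplicate mean alongside.

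**Cost.** Wording in both documents. Moving the ECG triplicate leaves the number of tracings unchanged, since two extra tracings move from Day 1 to Day 3. There may be one added BP occasion or, after collection, one extra table set.

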## **5.2. Study Conduct and Participant Disposition**

Subject disposition summaries will include the number of subjects who were screened for Part III, who were screen failures, who were run-in failures, who were enrolled, who were in each analysis population, and who completed the study. For percentages, the number of subjects screened will be the denominator for screen and run-in failures and for the Run-In Safety Population, which in turn will be the denominator for subjects enrolled. The number of subjects enrolled will be the denominator for the Safety and PK analysis populations and for subjects completing the study.

---

Reason for study discontinuation will be summarized by number and percentage of subjects for each reason reported; for the percentage, the number of subjects who discontinued will be the denominator.

Reason for screen failure will be summarized in a separate table by number and percentage of subjects for each reason reported; the denominator will be the number of screen failures.

### **5.3. Primary Endpoints Analysis**

#### **5.3.1. Definition of Endpoints**

The primary endpoints are incidence of TEAEs, maximum severity TEAEs, TEAEs related to study drug, treatment-emergent serious adverse events (TESAEs), and TEAEs leading to study discontinuation or death.

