14.9.1 Treatment-Emergent Adverse Events (TEAEs)

A TEAE is defined as an AE with start date/time at or after dosing with IMP. The number and percentage of subjects reporting TEAEs will be presented for each treatment by MedDRA system organ class (SOC) and preferred term (PT), each in descending order of frequency among all subjects in the given part of the study (then alphabetically in case of ties).

Incidence and number of study drug-related TEAEs, TESAEs, study drug-related TESAEs, TEAEs leading to death, TEAEs leading to IMP discontinuation, and TEAEs leading to IMP interruption will be presented both in an overall summary table and by SOC and PT. Included in the overall summary table will be incidence and number of severe TEAEs and TEAEs with grade 3 or higher toxicity grade (applicable for Parts I and II only). TEAE incidence will also be summarized by maximum severity within SOC and PT. Incidence of TEAEs will be summarized by PT only (not SOC) in descending order of incidence among all subjects (within study part).

In summaries by severity and relationship to study drug, if more than one TEAE is coded to the same PT for the same subject, the subject will be counted only once for that PT using the most severe/most related occurrence. Missing severity, toxicity, and relatedness will be queried until resolution.

Non-TEAEs and, for Part III, run-in AEs in the Run-In Safety Population will be summarized separately.

Separate listings will be presented for TEAEs, TESAEs, TEAEs leading to IMP interruption or discontinuation and TEAEs leading to death.

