**Table 2 Study Objectives and Estimands**

		Estimand		
Objective Clinical Category	Statistical Category	Variable/Endpoint	Pop-ulation	Population-Level Summary
Primary Objective				
Assess the safety and tolerability following repeated doses of INDV-2000 administered alone and with SUBOXONE sublingual (SL) film in an opioid use disorder (OUD) treatment seeking population.				
Adverse Events (AEs)	Primary	Incidence, severity, and relatedness of treatment-emergent adverse events (TEAEs), serious adverse events (SAEs) and events leading to study discontinuation or death.	Safety	Categorical descriptive

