### **5.5.2. Adverse Events**

A TEAE is an AE that started at or after first administration of IMP. A run-in AE is an AE that started at or after first administration of study drug during the run-in period. AEs will be assigned to study treatments based on start dates and times of treatments and start dates and times of AEs.

AEs will be coded to a System Organ Class (SOC) and Preferred Term (PT) using Medical Dictionary for Regulatory Activities (MedDRA). Additional details of the coding process, including the current version of the dictionary, are described in the Data Management Plan. All AEs will be listed for individual subjects. Listings will include SOC, PT, and reported term; treatment; onset date and time, end date, and duration; run-in status, treatment-emergence, severity, toxicity grade (though not required for Part III of the study), seriousness and seriousness criteria; relationship to study drug; action taken with IMP; action taken with SUBOXONE SL film; whether concomitant treatment was given; outcome; and whether the AE resulted in study discontinuation. Duration (days) is calculated as the AE end date – the AE onset date +1; for ongoing AEs, the date of end of study participation will be used as the end date. Duration will be missing if either the start or end date is partially or completely missing. SAEs, TEAEs leading to IMP discontinuation or interruption, AEs leading to SUBOXONE SL film discontinuation or interruption, and fatal AEs will be listed separately.

The incidence and number of all TEAEs, TESAEs, study drug-related TEAEs and TESAEs, severe TEAEs, TEAEs leading to IMP discontinuation or interruption, and fatal TEAEs will be presented in an overall summary table.

TEAEs, TESAEs, study drug-related TEAEs and TESAEs, and run-in AEs will be summarized by MedDRA SOC and PT, each in descending order of frequency among all subjects within study part (then alphabetically in case of ties). TEAEs will also be

summarized by maximum severity within SOC and PT. If an AE is reported more than once by a subject within a SOC and/or PT, the maximum reported level of severity will be used at each level of summation in the severity summary table.

Incidence and number of TEAEs will also be summarized by PT only (ie, not SOC), sorted by descending frequency among all subjects (within study part).

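### No table described in the SAP gives the incidence of TEAEs leading to study discontinuation, a primary endpoint component; the nearest item combines IMP discontinuation with interruption

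*SAP*

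**What the plan says.** **Endpoint.** SAP 5.3.1 lists "TEAEs leading to study discontinuation or death" among the primary endpoints. SAP Table 2 repeats it as "events leading to study discontinuation or death", with the Safety Population and a categorical descriptive summary. SAP 5.3.2 confirms the Safety analysis set. Protocol 14.7.1 speaks only of discontinuation and does not say whether from the study or from IMP.

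**Overall table.** SAP 5.5.2 ends its list of contents with "severe TEAEs, TEAEs leading to IMP discontinuation or interruption, and fatal TEAEs will be presented in an overall summary table". Study discontinuation is not in that list.

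**SOC/PT tables.** SAP 5.5.2 states: "TEAEs, TESAEs, study drug-related TEAEs and TESAEs, and run-in AEs will be summarized by MedDRA SOC and PT". No discontinuation category is included.

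**Where study discontinuation does appear.** The AE listing carries a field, "and whether the AE resulted in study discontinuation". In the disposition section (SAP 5.2), "Reason for study discontinuation will be summarized by number and percentage of subjects for each reason reported", with the subjects who discontinued as denominator.

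**Protocol plan.** Protocol 14.9.1 says that "TEAEs leading to IMP discontinuation, and TEAEs leading to IMP interruption will be presented both in an overall summary table" and also by SOC and PT.

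**Change log.** SAP Section 1 says that differences from the protocol are identified in Appendix 2. The visible text there records only the added Screened and Enrolled populations.

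**The concern.** The study has no hypothesis test, so the descriptive tables are the primary result. A primary endpoint component should be readable from a described table, in the stated population and with the stated denominator. Here the endpoint concerns leaving the study, while the nearest tabulated item concerns what happened to IMP and adds temporary interruptions.

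In a small open-label tolerability cohort, a permanent stop and a pause are different findings. The protocol treats them differently in Part III: the individual criteria in 6.5.1.3 discontinue the subject, while the study-level criteria in 6.5.1.4 pause the current cohort pending review. A combined percentage cannot be split again from the table, so it could be read as a discontinuation rate that it is not.

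**Working it through.** The documents give no figure to reproduce. The check sets the endpoint against each described output, then illustrates the possible size of the gap.

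**Step 1: does any described output return the endpoint?** The target is subjects with a TEAE leading to study discontinuation, divided by the Safety Population.

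- Overall AE summary (SAP 5.5.2): right population, but the item is IMP discontinuation or interruption. Fatal TEAEs have their own item, so the death half of the endpoint phrase is covered and the discontinuation half is not.
- SOC/PT, maximum-severity and PT-only tables (SAP 5.5.2): no discontinuation category.
- Summary of AEs that are neither treatment-emergent nor run-in (SAP 5.5.2): excludes TEAEs by definition.
- Disposition (SAP 5.2): counts reasons for study discontinuation, is not limited to TEAEs, and divides by discontinued subjects.
- AE listing (SAP 5.5.2): flags the right events but gives no incidence.

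None returns the endpoint as defined.

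**Step 2: how close is IMP discontinuation to the endpoint?** Protocol 6.6 counts permanent discontinuation of study drug as withdrawal from the study, and protocol 9.1 includes INDV-2000 in study drug. A separate IMP-discontinuation row would therefore come close to the endpoint. The material gap is the added interruptions.

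**Step 3: illustrative size.** N = 16 is the Part III maximum (protocol 14.2). The counts are assumed, because the documents give no expected numbers. Let d be subjects with a TEAE leading to permanent discontinuation, and i be other subjects with interruption only.

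- Endpoint = d / N. Combined item = (d + i) / N. Difference = i / N, or 1/16 = 6.25 percentage points per interrupted subject.
- d = 0, i = 2: endpoint 0/16 = 0%; combined item 2/16 = 12.5%.
- d = 1, i = 2: endpoint 1/16 = 6.25%; combined item 3/16 = 18.75%.
- d = 1, i = 0: both 1/16 = 6.25%.

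The two agree only when no subject has an interruption alone.

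**Step 4: the disposition denominator.** Assume 1 withdrawal for a TEAE among 4 discontinued subjects. Disposition shows 1/4 = 25%; the endpoint is 1/16 = 6.25%.

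**The case against.** The strongest reply has four parts.

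- **The information is there.** Disposition gives a count of subjects whose recorded reason is an adverse event, and the listing shows, for each event, the action taken with IMP and with SUBOXONE and whether the subject left the study. With at most 16 subjects the count can be found by hand. This stands and limits the consequence, but it does not supply a tabulated incidence for a declared primary endpoint.
- **The combined wording may be shorthand for two rows.** SAP 5.3.1 also joins study discontinuation and death in one phrase, yet fatal TEAEs get their own item. Protocol 14.9.1 joins interruption and discontinuation for its listing while separating them in tables. SAP 5.1.3 leaves table layouts to a separate document. This stands as a caveat: the shells may split the row, but the SAP text does not say so.
- **IMP discontinuation nearly equals study discontinuation.** Under protocol 6.6 this stands, which is why the point rests mainly on the interruptions.
- **An SOC/PT table of study discontinuations is more than the protocol asks.** This also stands. Protocol 14.9.1 plans SOC/PT tables for IMP discontinuation and for IMP interruption, not for study discontinuation.

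A reader might also infer that the combined item misses many withdrawals between Day 14 and Day 21, or withdrawals where only SUBOXONE was stopped. The documents give little support for either. Protocol 6.4 counts a Part III subject as completed after all INDV-2000 doses and the Day 14 safety assessments, so a later loss is not clearly a discontinuation. Stopping SUBOXONE permanently for an event is itself study withdrawal under protocol 6.6, so IMP would normally stop too. SUBOXONE overlaps INDV-2000 only on Days 3 to 9.

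**Conclusion.** The mismatch holds on the SAP text. A primary endpoint component has no described table giving its incidence in the Safety Population, and the nearest item combines two outcomes that the protocol separates. The SAP text also omits the protocol's SOC/PT tables for both. The visible part of Appendix 2 records neither change, though some of its content may be redacted.

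It would be too strong to say that the SAP yields no count of withdrawals for adverse events, or that the endpoint will be missing from the final outputs. Disposition and the listing carry the information, and the shells were not seen.

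The size depends on counts that the documents do not give: each subject with interruption only adds 6.25 percentage points at N = 16, and a smaller Safety Population would make each step larger. If no such interruption occurs, the combined item and a separate IMP-discontinuation row agree. The effect is on descriptive reporting only. The point deserves correction because it concerns the primary endpoint and the remedy is small.

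**What to change.** In SAP 5.5.2:

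- Add a row to the overall summary for TEAEs leading to study discontinuation, with the Safety Population as denominator.
- Show TEAEs leading to IMP discontinuation and TEAEs leading to IMP interruption as separate rows, as in protocol 14.9.1.
- Restore the SOC/PT tables for those two items, or record and justify their omission in Appendix 2.

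Check the table shells against the revised text. In the same edit, correct SAP 5.3.2, which sends the reader to Section 5.6.2 (Medical History) for AE summaries; they are in 5.5.2.

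The cost is a few table rows and SAP wording, plus the SOC/PT tables if restored. The listing already carries the study-discontinuation flag and the action taken with IMP, so no new data collection is needed.
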